Omeprazole/Esomeprazole D9612C00034			
study, evaluati lansoprazole 6	randomized, 4-treatming the effect of esome of mg on the pharmace healthy volunteers	prazole 40 mg, on				
Sponsor: AstraZene	ca AB, [name], S	weden				
The following Amen of preparation:	dment(s) and Administrative C	Changes have been made	to this protocol since the date			
Amendment No.	Date of Amendment	Local Amendment N	No: Date of Local Amendment			
Administrative Change No.	Date of Administrative Change	Local Administrativ Change No.	Date of Local Administrative Change			
		_				

Clinical Study Protocol

This submission /document contains trade secrets and confidential commercial information, disclosure of which is prohibited without providing advance notice to AstraZeneca and opportunity to object.

PROTOCOL SYNOPSIS

An open-label, randomized, 4-treatment, 3-period, crossover interaction study, evaluating the effect of esomeprazole 40 mg, omeprazole 80 mg or lansoprazole 60 mg on the pharmacodynamics and the pharmacokinetics of clopidogrel in healthy volunteers

Coordinating Principal Investigator

Study center(s) and number of volunteers planned

This protocol will be conducted utilizing from 1 to 3 study centers. Approximately 101 volunteers will be randomized in order to have 81 evaluable volunteers.

Study period		Phase of development
Estimated date of first volunteer enrolled	June 2010	Phase I
Estimated date of last volunteer completed	December 2010	

Objectives:

Primary objective

To assess the effect of esomeprazole 40 mg, omeprazole 80 mg, or lansoprazole 60 mg on the pharmacodynamic (PD) profile of clopidogrel by assessing maximum inhibition of platelet aggregation (mIPA) at Days 2, 6, 15 and 30 relative to baseline.

Secondary objectives

- To assess the effect of esomeprazole 40 mg, omeprazole 80 mg or lansoprazole 60 mg on the pharmacokinetic (PK) profile of clopidogrel active metabolite by assessing the AUC, AUC_{0-t} and C_{max} after the loading dose of clopidogrel (Day 1) and AUC_{0-t,ss} and C_{ss,max} at Days 5, 14, and 29.
- To evaluate safety and tolerability of clopidogrel given concomitantly with esomeprazole, omeprazole, or lansoprazole.

Exploratory objectives

- To assess the effect of esomeprazole 40 mg, omeprazole 80 mg or lansoprazole 60 mg on the PD profile of clopidogrel by assessing change in platelet reactivity index (ΔPRI), derived from flowcytometric assay (VASP) results, at Days 2, 6, 15, and 30 relative to baseline.
- To assess the effect of esomeprazole 40 mg, omeprazole 80 mg or lansoprazole 60 mg on the pharmacodynamic (PD) profile of clopidogrel excluding low responders (mIPA of 25% or less at Day 2 when receiving clopidogrel alone) by assessing maximum inhibition of platelet aggregation (mIPA) at Days 2, 6, 15 and 30 relative to baseline.

Study design

This is an open-label, randomized, 4-treatment, 3-period cross-over study designed to assess the PD and PK interaction between clopidogrel and esomeprazole, omeprazole or lansoprazole. Each volunteer will be randomized to receive a sequence of clopidogrel alone and two of the PPIs plus clopidogrel.

The reference treatment arm will consist of a clopidogrel loading dose of 300 mg administered on Day 1 and then clopidogrel 75 mg administered once daily for 28 days. The 3 test treatment arms will have the same clopidogrel dosing used in the reference treatment arm co-administered with either esomeprazole 40 mg, omeprazole 80 mg, or lansoprazole 60 mg once daily for 29 days. The route of administration is oral. The treatment periods will be separated by washout periods of at least 14 days. The randomization will be performed as a partially balanced design with 18 sequences, including clopidogrel alone in all treatment sequences.

Volunteers will be seen in the clinic for Screening (pre-entry) and Day -1 for clinic admission. Volunteers will be randomized on Day 1 (Treatment period 1 only) and visits for PD measurements will occur predose (baseline) and predose on Days 2, 6, and 15 as well as on Day 30 (24 hour after the Day 29 dose). Blood samples for quantitation of the active metabolite of clopidogrel will be taken prior to and 0.25, 0.5, 1, 1.5, 2, 4, and 6 hours after the first dose of clopidogrel on Day 1 and prior to and 0.25, 0.5, 1, 1.5, 2, and 4 hours after the clopidogrel doses on Days 5, 14 and 29. Volunteers will be admitted to the clinic on Days -1, 4, 13, and 28 and released on Days 2, 6, 15 and 30 after the scheduled PK and PD assessments are obtained. The total study duration is approximately 146 days which includes a 21 day preentry screening and a 7 day follow up visit.

Target volunteer population

The target population is healthy males within age of 18-45 years and females within age of 18-55 years and Body Mass Index (BMI = weight/height²) greater than or equal to 19 kg/m^2 and less than or equal to 30 kg/m^2 .

Outcome variable(s):

• Pharmacodynamic:

The primary endpoint of this study is maximum inhibition of platelet aggregation (mIPA) based on maximum platelet aggregation (mPA) to 20 μ M ADP assessed at baseline and on Days 2, 6, 15, and 30. In addition, VASP (flowcytometric VASP-assay) parameters of platelet reactivity index (PRI) and change in platelet reactivity index (Δ PRI), exploratory PD endpoints, will be assessed at these same time points.

• Pharmacokinetics:

AUC, AUC_{0-t}, and C_{max} will be calculated after the loading dose of clopidogrel on Day 1 and AUC_{0-t,ss} and $C_{ss,max}$ on Days 5, 14, and 29 for clopidogrel active metabolite.

• Safety:

Adverse events, vital signs, and safety laboratory variables will be assessed throughout the study.

Statistical methods

Plasma concentrations of clopidogrel active metabolite and the derived PK parameters will be summarized by treatment using descriptive statistics.

Both PD and PK variables will be analyzed using a linear mixed effect analysis of variance (ANOVA) model with fixed effect for period, sequence, site, and treatment and a random effect for volunteer within sequence. The clopidogrel alone treatment will be the reference for the 3 test interaction treatment arms.

Safety data will be presented with descriptive statistics. Adverse events will be summarized by incidence within treatment. Laboratory safety tests and vital signs will be summarized by treatment group and time points within treatment groups.

TABLE OF CONTENTS

PAGE

	TITLE PAGE	1
	PROTOCOL SYNOPSIS	2
	TABLE OF CONTENTS	5
	LIST OF ABBREVIATIONS AND DEFINITION OF TERMS	9
1.	INTRODUCTION	12
1.1	Background	12
1.2	Research hypothesis	12
1.3	Rationale for conducting this study	12
1.4	Benefit/risk and ethical assessment	14
2.	STUDY OBJECTIVES	14
2.1	Primary objective	14
2.2	Secondary objectives	14
2.3	Exploratory objectives	15
3.	STUDY PLAN AND PROCEDURES	15
3.1	Overall study design and flow chart	15
3.2	Rationale for study design, doses and control groups	20
4.	VOLUNTEER SELECTION CRITERIA	20
4.1	Inclusion criteria	20
4.2	Exclusion criteria	21
5.	STUDY CONDUCT	23
5.1	Restrictions during the study	23
5.2	Volunteer enrollment and randomization, and initiation of investigational	
5.2.1	product	25
5.2.1		20
3.3	Procedures for handling volunteers incorrectly enrolled, randomized or initiated on investigational product	27
5.4	Blinding and procedures for unblinding the study	27
5.5	Treatments	
5.5.1	Identity of investigational product(s)	
5.5.2	Doses and treatment regimens	28

Table 2	Laboratory variables					
Table 3	Volume of blood to be drawn from each volunteer					
LIST O	F FIGURES					
Figure 1	Study design17					
Figure 2	Treatment sequences					
LIST O	F APPENDICES					
Appendix	A Signatures					
Appendix	B Additional Safety Information					
Appendix	C International Airline Transportation Association (IATA) 6.2 Guidance Document					

LIST OF ABBREVIATIONS AND DEFINITION OF TERMS

The following abbreviations and special terms are used in this study Clinical Study Protocol.

Abbreviation or special term	Explanation
ADP	Adenosine diphosphate
AE	Adverse event
ALT	Alanine aminotransferase
AMC	active thiol metabolite of clopidogrel
ANOVA	Analysis of variance
AST	Aspartate aminotransferase
AUC	Area under the curve from time zero to infinity
$\mathrm{AUC}_{0\text{-t}}$	Area under the curve from time zero to last quantifiable concentration
AV	Atrioventricular block
BMI	Body mass index
BP	Blood pressure
CI	Confidence interval
C_{max}	Maximum observed concentration
CPA	Clinical Pharmacology Alliance
CK	Creatine kinase
CSP	Clinical Study Protocol
CSR	Clinical Study Report
CV	Coefficient of variation
CYP2C19	Cytochrome P450 2C19
DAE	Discontinuation of Investigational Product due to Adverse Event
DMP	Data Management Plan
DNA	Deoxyribonucleic acid
EDC	Electronic data capture
FSH	Follicle stimulating hormone
GCP	Good Clinical Practice
GMP	Good Manufacturing Practice
h	Hours
Hb	Hemoglobin

Abbreviation or	Explanation
special term	Explanation
HBsAg	Hepatitis B surface antigen
hCG	Human chorionic gonadotrophin
HIV	Human Immunodeficiency Virus
ICF	Informed Consent Form
ICH	International Conference on Harmonisation
IP	Investigational Product
IRB	Institutional Review Board
IUD	Intrauterine device
LIMS	Laboratory Information Management System
LLOQ	Lower Limit of Quantification
LSLV	Last Subject Last Visit
max	Maximum
NC	Not calculable
MedDRA	Medical Dictionary for Regulatory Activities
MI	Myocardial Infarction
min	Minimum
mIPA	Maximum inhibition of platelet aggregation
mPA	Maximum platelet aggregation
NSAID	Nonsteroidal anti-inflammatory drug
OAE	Other Significant Adverse Event
OTC	Over-the-counter
PCI	Percutaneous coronary intervention
PD	Pharmacodynamic
PR(PQ)	ECG interval measured from the onset of the P wave to the onset of the QRS complex.
PICTS	Phase I clinical trial system (brand name for Quintiles, Inc EDC)
pECG	Paper ECG
PK	Pharmacokinetic
PPI	Proton pump inhibitor
PRI	Platelet Reactivity Index
ΔPRI	Change from baseline in PRI
QRS	ECG interval measured from the onset of the QRS complex to the J point.

Abbreviation or special term	Explanation
QT	ECG interval measured from the onset of the QRS complex to the end of the T wave
QTc	QT interval corrected for heart rate
QTcF	QT interval corrected for heart rate using Fridericia's formula
RR	The time between corresponding points on 2 consecutive R waves on ECG
Rsq	Regression coefficient
SAE	Serious adverse event
SD	Standard deviation
SDV	Study data verification
SI	Système International
SOC	System organ class
SOP	Standard Operating Procedure
SS	Steady state
ST	ST interval of ECG
STEMI	ST segment elevation myocardial infarction
SUSAR	Suspected Unexpected Serious Adverse Reaction
$t_{1/2}$, Interval	Time interval of the log-linear regression to determine $t_{1/2}$
$t_{1/2}, N$	Number of data points included in the log-linear regression analysis
TEAE	Treatment-emergent adverse event
t_{max}	Time to maximum concentration
ULN	Upper limit of normal
VASP	Vasodilator-stimulated phosphoprotein

1. INTRODUCTION

1.1 Background

Clopidogrel is a platelet aggregation inhibitor approved for use in patients with a history of recent myocardial infarction (MI), recent stroke or established peripheral arterial disease, in patients with acute coronary syndrome, and in patients with ST-segment elevation myocardial infarction (STEMI). Its use is also recognized in US and European guidelines as the standard of care for patients with coronary stent placement. The widespread clinical usage of clopidogrel is based on studies that showed an important reduction in cardiovascular mortality and morbidity with clopidogrel (Smith et al 2006, Silber et al 2005). Most of these trials involved concomitant use of clopidogrel and aspirin (Yusuf et al 2001, Sabatine et al 2005, Steinhubl et al 2002, Chen et al 2005). Concomitant use of clopidogrel and aspirin has been associated with a significantly increased risk of bleeding. The bleeding has been generally accepted, since the benefits of concomitant therapy are substantial in terms of cardiovascular risk reduction. In recent years, the concomitant use of clopidogrel and aspirin has been strongly recommended in cardiology guidelines around the world, so bleeding has become a more common event.

Due to the common occurrence of acid related diseases patients with cardiovascular diseases commonly receive proton pump inhibitors (PPIs). In addition, in an effort to ameliorate the gastrointestinal side effects associated with clopidogrel, PPIs have in the past been routinely co administered with clopidogrel. Clopidogrel is administered as an inactive prodrug requiring metabolism by cytochrome P450 isozymes for its antiplatelet activity. A commonly prescribed PPI, omeprazole (when administered as a once daily 80 mg dose) has been shown to inhibit the conversion of clopidogrel to the active metabolite. Current prescribing information for clopidogrel includes a warning about its use with omeprazole.

The aim of this study is to determine if there is a pharmacological interaction between clopidogrel and different types of PPIs, and if the extent of this possible interaction would change over time.

1.2 Research hypothesis

The effect of PPI co-administration on the pharmacodynamics (PD) and pharmacokinetics (PK) of clopidogrel is not similar across this class of compounds but will differ based on the physical and chemical characteristics of each unique PPI.

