2. STUDY OBJECTIVES

2.1 Primary objective

To assess the effect of esomeprazole 40 mg, omeprazole 80 mg, or lansoprazole 60 mg on the pharmacodynamic (PD) profile of clopidogrel by assessing maximum inhibition of platelet aggregation (mIPA) at Days 2, 6, 15 and 30 relative to baseline.

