Pharmacokinetic comparison of test treatments (esomeprazole + clopidogrel, omeprazole + clopidogrel, or lansoprazole + clopidogrel) to the reference treatment (clopidogrel alone) will be assessed using the standard two one-sided t-tests approach. The PK parameters AUC, AUC_{0-t} and C_{max} for the clopidogrel active metabolite for each of the test treatments will be compared with the PK parameters for the reference treatment. Comparisons between the test and reference treatments will be made for each assessment day by using a mixed effects analysis of variance (ANOVA) model for each PK parameter (AUC, AUC_{0-t} and C_{max}). PK parameters will be analyzed on the natural log scale with fixed-effects for treatment, period, site, and sequence. Volunteers within sequence will be included as a random effect in the model. The linear contrasts subtracting the least-squares means for the reference treatment from the least-squares means for the test treatment will be estimated and exponentiated to obtain least square estimates of the ratios of geometric means and the corresponding 90% CI.

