12.2.5 Pharmacodynamics

Descriptive statistics will be used to summarize mPA, and mIPA, in volunteers by treatment and by day. In addition, VASP data (PRI and Δ PRI) will be summarized using descriptive statistics by treatment and by day. All PD variables will be presented in listings.

Pharmacodynamic comparison of test treatments (esomeprazole + clopidogrel, omeprazole + clopidogrel, or lansoprazole + clopidogrel) to the reference treatment (clopidogrel alone) will be assessed for each of the PD endpoints – mIPA and Δ PRI. These PD endpoints for each of the test treatments will be compared with the corresponding PD endpoints for the reference

treatment. Comparisons between the test and reference treatments will be made by using a mixed effects analysis of variance (ANOVA) model with fixed-effects for treatment, period, site, and sequence. Volunteers within sequence will be included as a random effect in the model. Log-transformations may be used to meet model assumptions. The linear contrasts subtracting the least-squares means for the reference treatment from the least-squares means for the test treatment will be estimated to obtain least square estimates of the difference in least square means and the corresponding 90% CI. P-values will also be presented.

The above analysis will be repeated on mIPA excluding volunteers defined as clopidogrel low responders (mIPA response of 25% or less at Day 2) when receiving clopidogrel alone.

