12.3 Determination of sample size

The study is sized to estimate the absolute mean difference in mIPA with and without the PPI with a specified precision. With 54 volunteers, a 95% CI with length of at most 9 percentage units is achieved with at least 96% probability. As each of the 3 PPIs is included in two-thirds of the planned treatment sequences, a total of 81 volunteers are required. Assuming a 20% dropout rate for this study, 101 volunteers will be enrolled to ensure 81 volunteers complete the study.

The calculation assumes an SD of paired difference of 14% units, derived from the root MSE of the analysis of internal data on ADP-induced maximum extent IPA for %mIPA (20 μ M ADP).

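### The research hypothesis is that the PPIs differ from one another, but every planned contrast is PPI versus clopidogrel alone, so that hypothesis is not tested

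*Protocol*

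**What the plan says.** Section 1.2 is the only place where the protocol states a hypothesis, and it is about differences between PPIs: the effect of co-administration "is not similar across this class of compounds but will differ based on the physical and chemical characteristics of each unique PPI".

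The comparisons are fixed elsewhere, and all run against clopidogrel alone:

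- Synopsis, statistical methods: "The clopidogrel alone treatment will be the reference for the 3 test interaction treatment arms".
- Section 12.2.4 (PK): the parameters "for each of the test treatments will be compared with the PK parameters for the reference treatment".
- Section 12.2.5 (PD): "These PD endpoints for each of the test treatments will be compared with the corresponding PD endpoints for the reference" treatment, and "The linear contrasts subtracting the least-squares means for the reference treatment from the least-squares means for the test treatment will be estimated", with 90% CIs and p-values. The analysis without low responders repeats these contrasts.
- Section 12.3: "The study is sized to estimate the absolute mean difference in mIPA with and without the PPI with a specified precision".

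The primary objective in section 2.1 is likewise about each PPI's effect on clopidogrel: "To assess the effect of esomeprazole 40 mg, omeprazole 80 mg, or lansoprazole 60 mg on the pharmacodynamic (PD) profile of clopidogrel". No section plans a PPI-versus-PPI contrast or a test of equality among the three PPI arms.

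**The concern.** A hypothesis that the PPIs differ needs a comparison between PPIs. Three separate comparisons with a common reference do not supply one. If one PPI reaches significance against clopidogrel alone and another does not, that is not evidence that the two differ.

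With p-values reported for the three reference contrasts and nothing reported between PPIs, a reader who returns to section 1.2 may well line up the significant and non-significant results. A claim that the class is or is not uniform could then rest on chance. The design already collects the information for a proper comparison, because each volunteer receives two PPIs.

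**Working it through.** **1. The protocol's own sizing.** Section 12.3 states: "With 54 volunteers, a 95% CI with length of at most 9 percentage units is achieved with at least 96% probability", with an SD of the paired difference of 14. The check is P(2·t(0.975, n−1)·S/√n ≤ 9), where (n−1)S²/14² follows a chi-square distribution with n−1 df. At n = 54 this gives 0.967, so the stated figure reproduces. Then 54/(2/3) = 81 evaluable volunteers. This sizing concerns PPI versus clopidogrel alone only.

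**2. Information on PPI pairs.** In Figure 2 each PPI appears with clopidogrel alone in 12 of 18 sequences (54 of 81 volunteers). Each pair of PPIs appears together in 6 of 18 (27 of 81). Every treatment is spread evenly over the three periods, so adjusting for period costs no precision on treatment contrasts.

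**3. Variances from the planned model.** Take 81 completers, three periods and within-volunteer variance σ². The information matrix for the three PPI effects relative to clopidogrel alone has 54 × (1 − 1/3) = 36 on the diagonal and −27/3 = −9 off it. Its inverse has 1/30 on the diagonal and 1/90 off it. Hence:

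- Var(PPI − clopidogrel alone) = σ²/30
- Var(PPI − PPI) = 2(1/30 − 1/90)σ² = 2σ²/45, which is 4/3 as large
- correlation between two PPI-versus-reference estimates = (1/90)/(1/30) = 1/3

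**4. Expected precision.** Section 12.3 calls 14 the SD of a paired difference but derives it from a root MSE, so both readings are shown. Residual df = 243 − 81 − 2 − 3 = 157 and t = 1.975.

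| Reading of 14 | σ | Contrast | SE | 95% CI length | 90% CI length |
|---|---|---|---|---|---|
| SD of paired difference | 14/√2 = 9.9 | PPI − reference | 1.81 | 7.1 | 6.0 |
| SD of paired difference | 9.9 | PPI − PPI | 2.09 | 8.2 | 6.9 |
| Within-volunteer SD | 14 | PPI − reference | 2.56 | 10.1 | 8.5 |
| Within-volunteer SD | 14 | PPI − PPI | 2.95 | 11.7 | 9.8 |

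On the first reading, a PPI − PPI 95% CI is no longer than 9 points with probability about 0.95, just short of the 96% stated for the main contrast. On the second it misses the 9-point target. Using only the 27 volunteers who receive both PPIs, with an SD of 14, the expected length would be about 11.1 points. The model does better because it also links the PPIs through clopidogrel alone.

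**5. Disagreement when the PPIs are identical.** Three estimates were simulated with the same true effect, SE 1.81 and pairwise correlation 1/3. The table gives the share of trials in which some but not all of the three tests are significant at two-sided 5%.

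| Common true effect (points of mIPA) | 4 | 5 | 6 | 7 | 8 |
|---|---|---|---|---|---|
| Tests disagree | 57% | 41% | 20% | 7% | 2% |

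The protocol gives no expected effect on mIPA, so these effect sizes are assumptions. If significance is read from the planned 90% CIs, the figures at 4, 5 and 6 points are about 49%, 29% and 12%. A single direct PPI − PPI test at the 5% level would be falsely significant about 5% of the time in the same setting.

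**The case against.** The strongest reply is that the objectives and the analysis agree. The aim (stated in sections 1.1 and 1.3), all objectives in section 2 and the sizing concern each PPI against clopidogrel alone, and sections 12.2.4 and 12.2.5 deliver that. The outlier is one sentence in the Introduction, which rewording would cure. This stands, and it limits the weight of the point: no objective goes unanswered and no planned estimate is biased.

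A reader might infer that the trial, followed as written, would declare the PPIs different by comparing significance. The document does not support that. It contains no such decision rule, and it reports effect estimates with CIs as well as p-values, so comparing significance is not the only way to look across the PPIs. Side-by-side intervals are still not a test of the difference.

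The disagreement rate is high only where power is intermediate; by 8 points it is about 2%.

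Pairwise contrasts would also not isolate the compounds. Section 3.2 gives the arms different roles and dose rationales: omeprazole as positive control, lansoprazole as probe, esomeprazole at an approved dose. A contrast therefore compares regimens, and the part of section 1.2 that attributes differences to the properties of each compound stays out of reach.

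Finally, an analysis plan that is not shown could add contrasts. It could, but the protocol has itself named the model, the reference and the contrasts, and those do not address its hypothesis.

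**Conclusion.** The point holds as an inconsistency within the protocol: section 1.2 states a between-PPI hypothesis, and no specified contrast tests it. It does not extend to the objectives, which the analysis answers.

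The risk lies in later interpretation. If section 1.2 were judged on which PPIs reach significance, identical PPIs would give discordant results in roughly 20% to 57% of trials for common effects of 4 to 6 points, falling to 2% at 8. This assumes 81 completers, a within-volunteer SD of 9.9 and two-sided 5% tests. If 14 is the within-volunteer SD, disagreement at 5 points rises to nearly 60%.

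The planned model can estimate the missing contrasts with no added volunteers, with 95% CIs of about 8.2 or 11.7 points depending on what the 14 represents.

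**What to change.** Add to sections 12.2.4 and 12.2.5 the three pairwise contrasts (omeprazole − esomeprazole, omeprazole − lansoprazole, esomeprazole − lansoprazole) from the same mixed model:

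- Give CIs at the level used for the other contrasts, as differences for PD and as ratios of geometric means for PK.
- Label them secondary or exploratory, and as comparisons of the PPI regimens at the studied doses.
- State that section 1.2 is assessed on these contrasts and not on differences in significance against clopidogrel alone.
- State the expected precision for mIPA: a 95% CI of about 8.2 points if 14 is the SD of the paired difference, about 11.7 if it is the within-volunteer SD.

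The cost is three contrast statements per model and a short paragraph, with no extra volunteers or samples. The small downside is a set of additional contrasts for which the study was not sized and which carry no multiplicity control; the text should say so.

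If the sponsor prefers not to add them, section 1.2 should be reworded to match the objectives, and the report should make no claim about differences between PPIs.
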